### **Statistical methods and analysis plan**

Differences in the concentrations of individual host biomarkers between participants with TBM disease and those without TBM shall be evaluated by the Mann–Whitney U-test for non-parametric data analysis or the students t test, if data is normally distributed. P-values shall be deemed significant if less than 5%. The diagnostic accuracy of individual host biomarkers shall be investigated by receiver operator characteristics (ROC) curve analysis. The predictive abilities of combinations of analytes (biosignatures) shall be investigated by General discriminant analysis (GDA), random forests, and other biomarker analysis techniques, following the training/test set approach as done in previous studies . For Flow cytometry data, cell gating and data analysis will first be carried out on FlowJo software (Oregon, USA), followed by parametric (t-test) or non-parametric (Mann-Whitney U-) tests to assess the differences in quantities of immune cell

subpopulations, intra and extracellular cytokines and other biomarkers among children with TBM and those with other meningitis. Kruskall-Wallies test or one-way ANOVA with post-hoc analysis will be performed for comparison of more than 2 groups as advised by bioinformaticians from the Division of Molecular Biology and Human Genetics.

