### **3. Inclusion and exclusion criteria:**

All children between the ages of 3 months and 13 years with suspected meningitis, and who require CSF examination for routine diagnostic purposes at Tygerberg Children's Hospital, where written consent is obtained will be included. If possible, assent will be obtained in those children older than 7 years who have a normal level of consciousness, i.e. a Glasgow Coma Score (GCS) of 15/15. Children 13 years and older will be excluded from the study. Failure to obtain written consent will also exclude children from the study.

The anticipated study period is November 2016 to December 2025. The estimated sample size, using a two-sample comparison of proportions (STATA®-Statistics/Data Analysis), required for each of the diagnostic aims of the study includes, at least, 72 children with definite or probable TBM and a total sample size of up to 460 patients (This includes children with TBM, bacterial

meningitis, viral meningitis and normal CSF). An average of 40 new TBM cases is admitted to our wards annually.

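### Single markers judged normal are compared by Student's t test with no provision for unequal variances, so with unequal group sizes the stated 5% level may not hold, in either direction (minor; cheap to improve)

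*Combined protocol and SAP*

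**What the plan says.** The section Statistical methods and analysis plan sets out the single-marker comparison as "Differences in the concentrations of individual host biomarkers between participants with TBM disease and those without TBM". The test is Mann-Whitney, "or the students t test, if data is normally distributed". The threshold follows: "P-values shall be deemed significant if less than 5" per cent. For the flow cytometry data, gating is "followed by parametric (t-test) or non-parametric (Mann-Whitney U-) tests". Comparisons of more than two groups use Kruskal-Wallis or one-way ANOVA.

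Nowhere does the plan mention equal variances, a check of variances, or Welch's version of either test. It also does not say how normality will be judged.

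Group sizes come from section 3, Inclusion and exclusion criteria, which asks for "at least, 72 children with definite or probable TBM and a total sample size of up to 460 patients". The total also covers children with bacterial or viral meningitis and children whose CSF is normal. No allocation between TBM and non-TBM is fixed.

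**The concern.** Student's t test, in the usual meaning of the name, pools the two sample variances and assumes they are equal. A marker can be normal in both groups and still differ in spread, so a condition on normality does not protect the assumption that matters here. With equal group sizes, pooling does little harm. With unequal sizes, the pooled variance is dominated by the larger group. The standard error is then too small if the smaller group is the more variable one, and too large if it is the less variable one.

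Equal spread is not something to take for granted when one diagnosis is compared with a mixture of three other categories. At stake is whether the reported single-marker p-values mean what the 5% threshold says. They could be too liberal, or they could cost power for real differences.

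**Working it through.** **Inputs**
- Nominal level 5% (Statistical methods and analysis plan). Sidedness is not stated; two-sided is assumed.
- n1 = 72 TBM, a stated minimum. Total 460, a stated maximum. So n2 = 460 − 72 = 388, and 388/72 = 5.4.
- TBM accrual: "An average of 40 new TBM cases is admitted to our wards annually". November 2016 to December 2025 is 110 months, and 110/12 × 40 ≈ 367 admissions. These are admissions, not enrolments, but they show that the split could be milder than 72 v 388, equal, or reversed.
- SD ratio r = TBM SD / non-TBM SD. The documents give no marker SDs, so r is an assumption, shown over 0.5 to 2.

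**Formula** (large-sample form, normal data, equal means, non-TBM SD set to 1)
- Variance the pooled test uses: Vp = [(n1 − 1)r² + (n2 − 1)]/(n1 + n2 − 2) × (1/n1 + 1/n2)
- True variance of the mean difference: Vt = r²/n1 + 1/n2
- Type I error ≈ 2 × [1 − Φ(c × √(Vp/Vt))], where c = 1.965 is the t critical value on 458 df

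**The plan's own figure.** At r = 1, Vp = Vt, and simulation from the exact distributions of the mean difference and the two variances gives 5.0%. The stated level is reproduced when spread is equal.

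**Two cases at 72 v 388**
- r = 2: Vp = (71 × 4 + 387)/458 × (1/72 + 1/388) = 1.4651 × 0.016466 = 0.02412. Vt = 4/72 + 1/388 = 0.05813. √(Vp/Vt) = 0.644, c × 0.644 = 1.266, error 20.6%.
- r = 0.5: Vp = (71 × 0.25 + 387)/458 × 0.016466 = 0.01455. Vt = 0.25/72 + 1/388 = 0.00605. √(Vp/Vt) = 1.551, c × 1.551 = 3.048, error 0.2%.

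**Type I error of the pooled t test at nominal 5%** (simulated; the formula agrees to about 0.1 percentage point)

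| TBM v non-TBM | r = 0.5 | 0.8 | 1 | 1.25 | 1.5 | 2 |
|---|---|---|---|---|---|---|
| 72 v 388 | 0.2% | 2.3% | 5.0% | 9.2% | 13.5% | 20.6% |
| 100 v 360 | 0.5% | 2.7% | 5.0% | 8.4% | 11.6% | 16.9% |
| 150 v 310 | 1.6% | 3.4% | 5.0% | 7.0% | 8.7% | 11.3% |
| 230 v 230 | 5.0% | 5.0% | 5.0% | 5.0% | 5.0% | 5.0% |
| 360 v 100 | 16.9% | 8.3% | 5.0% | 2.7% | 1.5% | 0.5% |

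Welch's t test gives 5.0% (to within 0.1 point) in every cell.

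**Power at 72 v 388.** For a difference at which Welch has 80% power, the pooled test has 41% at r = 0.5 and 60% at r = 0.67. At r = 1 it has 80.6%, against 80.0% for Welch.

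**The Mann-Whitney branch.** It is not a remedy for unequal spread. At 72 v 388 with equal centres, it rejects in 0.9%, 8.9% and 11.6% of runs at r = 0.5, 1.5 and 2.

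**The case against.** The other side has a good deal to say, and most of it limits the point rather than removing it.

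- **Real error rate.** A reader might infer that the 5% threshold really runs at 13% or more and that false markers will fill the candidate list. The documents do not support this. They give no SDs, and the inflated figures need TBM to be both the smaller and the more variable group, with exactly equal means. A marker unrelated to TBM has the same distribution in both groups, and then both planned tests hold about 5%.
- **Direction.** Pooling several conditions in the non-TBM group adds between-condition variance to what may be the larger group. That pushes towards the conservative side. Neither direction can be presumed.
- **Sizes.** 72 v 388 is a corner: a minimum set against a maximum. The figure 388 is derived, not stated, and milder or reversed splits are possible.
- **Reach.** Mann-Whitney is listed first, and raw concentrations may seldom look normal. With assumed lognormal data at 72 v 388, both groups passed a Shapiro-Wilk check in 0.8% of runs at a log-SD of 0.2, and in none at 0.3 or above. The plan names no normality test, so how often the t test would be used is unknown.
- **Role of the p-values.** A reader might also infer that these tests select the markers for later modelling. The plan does not say so. Accuracy rests on ROC curves and on multi-marker models with training and test sets, and the first two aims centre on signatures named in advance.
- **Wording.** That Student's test is the pooled one is read from its name. The flow cytometry sentence says only that a t test is used.

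What these arguments do not supply is any provision for unequal variances. The plan has none, and only equal groups or equal spread would make one unnecessary.

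**Conclusion.** The point holds in a limited form. The plan makes Student's t test conditional on normality alone, in a design whose groups may be very unequal, so the stated 5% is not assured for markers that take that branch. Under the assumed SD ratios of 0.5 to 2, the level at 72 v 388 lies anywhere from about 0.2% to 21%, and at 150 v 310 from about 1.6% to 11%. With equal groups it stays at 5%.

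These figures rest on normal data, equal means, a two-sided test, the pooled reading of the test's name, and SD ratios that the documents do not give. The actual error in this study is therefore unknown in both size and direction. The consequence is confined to the reported single-marker p-values and the flow cytometry t tests; the ROC and biosignature results are unaffected. Severity is minor, and this is a cheap improvement to the analysis wording.

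**What to change.** In Statistical methods and analysis plan, replace Student's t test by Welch's t test, for example on log concentrations, for both the single markers and the flow cytometry comparisons. Replace one-way ANOVA by Welch ANOVA. State one method in advance for all markers, and do not let a normality check choose between methods. If a rank-based method is preferred, the Brunner-Munzel test is acceptable. So is a test of AUC = 0.5 with a DeLong standard error, which has the advantage of matching the planned ROC analysis.

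The cost is a change of wording only: no extra children, samples or assays, and all these tests are in standard software. When variances are equal, the loss of power is negligible (80.0% for Welch against 80.6% for the pooled test at 72 v 388). On the log scale the comparison is of geometric rather than arithmetic means, and the text should say so.

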## **Aims**

The main aims of the proposed project are as follows:

- 1) To validate a previously identified and patented three-marker CSF biosignature (IL-13, VEGF, cathelicidin LL37) for the diagnosis of TBM, in a new cohort of children with suspected TBM
- 2) To evaluate the usefulness of a recently identified and patented adult seven-marker serum protein biosignature (CRP, serum amyloid A, apolipoprotein A-1, transthyretin, complement factor H, interferon-gamma and IP-10) and other recently identified host markers, as a tool for the diagnosis of TBM
- 3) To investigate the usefulness of whole blood RNA transcripts as biosignatures for the diagnosis of TBM
- 4) To characterize the site of disease (CSF) versus peripheral blood immune profile of children with TBM, the response of immune cells to stimulation with *M.tb* antigens and explore differences between such responses in children with and those without TBM as part of student projects.
- 5) To develop a prototype point-of-care test based on host inflammatory protein biomarkers for

the rapid diagnosis of TBM (e.g. at the bedside) in children suspected of having TBM.

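### Individual markers get ROC analysis with no cut-off rule and no internal validation, so accuracy quoted at a cut-off, or for a best marker, chosen on the same children would be optimistic

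*Combined protocol and SAP*

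**What the plan says.** The combined protocol and SAP, under Statistical methods and analysis plan, treats single markers and combinations in two consecutive sentences.

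- Single markers: "The diagnostic accuracy of individual host biomarkers shall be investigated by receiver operator characteristics (ROC) curve analysis".
- Combinations: "The predictive abilities of combinations of analytes (biosignatures) shall be investigated by General discriminant analysis (GDA), random forests, and other biomarker analysis techniques", and these are to be developed "following the training/test set approach as done in previous studies".

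The validation clause belongs to the second sentence only. For a single marker the plan does not name the data set, a cut-off rule, a split, cross-validation or a bootstrap.

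Under Aims, aim 2 covers the adult seven-marker serum signature "and other recently identified host markers, as a tool for the diagnosis of TBM". The number of these further markers is not given. Section 3 (Inclusion and exclusion criteria) sets a minimum of "72 children with definite or probable TBM and a total sample size of up to 460 patients".

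**The concern.** A cut-off chosen because it performs best on a set of children, then scored on those same children, gives apparent accuracy. Part of that performance is chance and will not recur in new patients. Singling out the best of many markers on the same data adds a second layer of the same bias, and this layer also inflates the AUC of the selected marker.

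The plan accepts this principle for combinations but does not extend it to single markers. Single markers matter here: aim 2 evaluates an open list of them for diagnosis, aim 5 is a prototype bedside test, and Ethical concerns and consent says that markers validated in the project will be built into the prototype platform. A test that returns positive or negative needs a cut-off, so single-marker sensitivity and specificity are a foreseeable output. If they appear uncorrected beside held-out figures for signatures, the two sets will not be on the same footing.

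**Working it through.** **The plan's own figure.** The 72 and 460 in section 3 come from a two-sample comparison of proportions, but the two proportions, power and allocation ratio are not given, so they cannot be reproduced uniquely. Several inputs give 72 per group: for example 0.70 v 0.90 at 80% power with continuity correction, or 0.55 v 0.80 at 90% power without it (both two-sided 5%, 1:1). The point does not depend on which was used.

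**Inputs from the documents.** At least 72 TBM cases and a total of up to 460, hence up to 460 − 72 = 388 non-TBM children if exactly 72 have TBM.

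**Assumptions, none of them in the documents.** A binormal marker with equal variances; the true AUC; the cut-off rule; the number of candidate markers and their correlation.

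**Formulas.** Non-TBM values are N(0,1) and TBM values N(d,1), with d = √2·Φ⁻¹(AUC). The cut-off t is chosen on the simulated data. Apparent sensitivity and specificity are the observed proportions at t. The true values of that same cut-off are Φ(d − t) and Φ(t). Optimism is apparent minus true.

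**One marker, Youden cut-off, 72 v 388 (4,000 replicates):**

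| True AUC | Sensitivity, apparent v true | Difference | Specificity, apparent v true | Difference |
|---|---|---|---|---|
| 0.60 | 0.611 v 0.555 | 5.6 points | 0.585 v 0.575 | 1.0 |
| 0.70 | 0.675 v 0.628 | 4.7 | 0.656 v 0.648 | 0.8 |
| 0.80 | 0.752 v 0.711 | 4.1 | 0.733 v 0.726 | 0.7 |
| 0.90 | 0.840 v 0.806 | 3.4 | 0.824 v 0.818 | 0.6 |

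The bias falls mainly on sensitivity because the TBM group is the smaller one.

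**Same marker, cut-off fixed at 95% specificity.** Sensitivity is 0.329 v 0.325 at AUC 0.80 and 0.567 v 0.564 at AUC 0.90. Across all AUCs the excess is at most 0.4 points for sensitivity and 0.2 for specificity.

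**AUC of one pre-named marker.** The mean estimates are 0.600, 0.699, 0.800 and 0.900 for true values 0.60, 0.70, 0.80 and 0.90, so there is no bias.

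**More TBM cases (assumed splits of 460).** With 150 v 310 the sensitivity excess is about 2.3 to 3.5 points for AUC 0.85 down to 0.60. With 230 v 230 it is about 1.5 to 2.5. With equal groups specificity carries the same amount by symmetry, so the sum is over by about 3 to 5 points.

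**Best of many, 72 v 388, Youden index (sensitivity + specificity − 1), apparent v true:**

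- 10 equally good independent markers, AUC 0.70: 0.419 v 0.281, a difference of 13.8 points.
- 30 equally good independent markers, AUC 0.65: 0.377 v 0.208, a difference of 16.9 points.
- The same settings with pairwise correlation between 0.3 and 0.8: roughly 10 to 15 points.
- One marker at AUC 0.85 and the rest at 0.65: about 4.4 points, which is no more than for a single marker.
- The AUC of the selected marker is also raised: the best of 10 to 40 independent markers with true AUC 0.70 shows 0.75 to 0.77.

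**Does held-out scoring remove the cut-off bias?** With an assumed 50/50 split, the test-half sensitivity/specificity is 0.623/0.648, 0.701/0.729 and 0.801/0.820 at AUC 0.70, 0.80 and 0.90. These values show no upward bias against the true values in the table.

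**The case against.** A reader might infer several stronger things that the documents do not support.

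- **That the ROC curves use all children.** The plan names no data set for them.
- **That single-marker sensitivity and specificity are overstated as planned.** No single-marker cut-off is announced and no Youden rule appears. ROC analysis is often summarised by the AUC, which is unbiased for a pre-named marker.
- **That the 52% sensitivity and 95% specificity in the literature review show how single markers will be reported.** Those figures belong to the three-marker CSF signature. They also describe a high-specificity operating point, and at a cut-off fixed there the bias almost disappears.
- **That single markers will be compared with held-out signatures to choose what goes into the device.** No section says so. The hypothesis, aim 1, the first part of aim 2 and aim 3 concern signatures, and the prototype is itself to be evaluated.

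All four limits stand, so the point is conditional. The size also needs perspective. Sensitivity of 71% read against 67% true (AUC 0.75) is smaller than the sampling error: 1.96·√(0.67·0.33/72) ≈ 0.11, or about 11 points either way. And 72 is a minimum; about 40 new TBM cases a year over a period from 2016 to 2025 makes more cases plausible.

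It may also be said that the earlier studies cited for the training/test approach dealt with this. Those sources are not part of the documents, and the citation is attached to combinations.

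What remains is that nothing in the plan prevents same-data scoring of single markers or selective emphasis on the best one. Sampling error does not excuse this, because a confidence interval centred on an optimistic estimate does not show the bias.

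**Conclusion.** The point holds in conditional form. The plan leaves single-marker accuracy without the validation that it requires for combinations. Any sensitivity and specificity quoted at a cut-off chosen on the same children, or for a marker picked as best on them, would be optimistic.

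For one marker the effect is modest and depends on the cut-off rule: a few points of sensitivity with a Youden cut-off at the planned minimum, next to nothing at a fixed 95% specificity. Best-of-many selection is the larger risk, but its size depends on how many markers are measured, how correlated they are and whether one stands out. The plan states none of these. All magnitudes rest on the binormal model.

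Aim 1, which validates a combination, is not touched. The change is worth making because it is a better method at very little cost, not because a main result is in danger.

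**What to change.** Add to Statistical methods and analysis plan:

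1. AUC with 95% CI will be reported for every marker measured, not only the best.
2. Where single-marker sensitivity and specificity are reported, the cut-off rule (for example a fixed specificity or the Youden index) is stated in advance.
3. Those figures come either from a cut-off set in the training children and scored in the held-out children, or from a bootstrap or cross-validation of the whole procedure, including the choice of cut-off and of marker.

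This needs no extra children or samples. The cost is a few sentences in the plan, a little more analysis, and single-marker figures that will be slightly lower and less precise. The bootstrap or cross-validation route loses less precision than a single split when TBM cases are few.

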There are not many studies in literature that specifically employed multiplex cytokine detection platforms in the search of host biomarkers specifically for TBM. In a recently patented and published study conducted by our research group , we investigated the usefulness of some of the host markers that we identified in our previous studies as diagnostic candidates for TBM. A three-marker CSF biosignature comprising of IL-13, VEGF and cathelicidin LL-37, diagnosed TBM with a sensitivity of 52%, specificity of 95%, with positive and negative predictive values of 91% and 66% respectively . In other biomarker studies, specifically investigating the use of whole blood RNA biosignatures in the diagnosis of TB disease, it was shown that host blood-based RNA transcripts might be useful in the diagnosis of active TB disease in both adults  and children . Furthermore, a recent study identified blood RNA signature that showed potential as a biosignature for the risk of developing active TB disease . However, none of these studies have been conducted specifically in children with TBM and it is not known, whether simple blood RNA signatures such as the ones already identified for pulmonary TB might be useful in this disease. The overall aim of the current study is therefore to assess the utility of ex vivo blood and CSF based host cytokine biomarkers and RNA transcripts as diagnostic tools for TBM. We would specifically be validating the diagnostic accuracy of our previously established 3-marker TBM CSF biosignature, evaluate other new host markers which have shown potential in adult studies

but which have not been investigated in children, in more children with TBM and also RNA signatures in blood samples collected from the same children. At the conclusion of the proposed study, the validated blood-based biosignatures identified in the present study shall be ready for possible incorporation into rapid, point-of-care diagnostic tools such as the one currently being developed for adult pulmonary TB by our research group ([www.screen-tb.eu](http://www.screen-tb.eu)).

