used to subtract background DNA found on the skin, during sequence analysis for the microbiome aspects of the study (aim 4). About 5 mL of CSF (3-7ml would be aimed for dependent on age and ease of lumbar puncture), shall be collected into sterile cryo tubes (Greiner bio-one) for use for research purposes, depending on how much is left over after specimens required for routine diagnosis have been collected. It must be stressed that although it is known that collection of up to 10ml of CSF in children with TBM may be beneficial in relieving of the pressure on the brain, hence help with alleviation of the symptoms, the amount of CSF collected will depend on the age, clinical presentation of the child, and whether collection of the specimen (3 to 7mL) will be beneficial to the child as determined by the specialist neurologist or medical practitioner treating the child. This will be followed by the collection of 1ml of whole blood into a serum blood tube and 2.5ml into a paxgene blood RNA tube, for the isolation of messenger RNA for future gene expression studies (aim 3). Furthermore, an additional 1 ml of blood will be collected from a subset of children for investigation of immune cells (whole blood intracellular staining by Flow cytometry; aim 7). Whether such an additional blood specimen is collected will depend on the judgement of the treating clinician and specialist paediatric neurologist, with the child's wellbeing always taking priority over the research. Where possible, mid-stream urine will be collected into sterile collection tubes for diagnostic analysis as part of aims 5 and 6. Therefore, depending on the judgement of the clinician and specialist paediatric neurologist, a total of up to 5mL (3 to 7ml) of extra CSF and up to 4.5ml of whole blood and up to 5 mL of urine (where possible) shall be collected from each consenting study participant for the purposes of this study. The proposed procedure (blood and CSF collection) was used in previously approved and now completed studies which provided samples for the pilot studies leading to this validation study (**HREC ref no: N11/01/006**, Principal Investigator, [name]; and **Ref no: N09/10/265**, Principal Investigator, Dr [name]).

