After collection of specimens for routine diagnostic purposes, the proposed research specimens shall be collected from consenting study participants and sent to the SUN Immunology Research laboratory, Fourth Floor, Education Building, where processing of these specimens shall occur. The CSF samples shall be centrifuged, aliquoted into 250 $\mu$ l amounts and frozen at minus 80 degrees until used for biomarker analysis using the Luminex technology, as was done in the pilot study (33). If more than 1mL of CSF is available, aliquots of the CSF will be used for immune cell

analysis by flow cytometry as mentioned above. Similarly, the 1ml of blood collected into a serum tube shall be centrifuged and serum harvested and stored at minus 80 degrees until used for biomarker analysis. The additional 1ml of blood, if collected, will also be used for flow cytometry as part of a student project. For the Paxgene blood, the tubes shall be frozen and when needed for use, RNA shall be isolated using the Paxgene blood RNA isolation kit. We will then use downstream techniques including quantitative Real Time PCR or other suitable technique to look at the usefulness of the RNA blood biosignatures already described in publications such as references (34-36), and also new signatures in the diagnosis of TBM. All sample processing shall be done according to standard laboratory procedures which are currently used in the SANAS accredited SUN-IRG laboratory.

Both the CSF and urine for metabolomics, up to 2ml and 5ml respectively, will be transported to the metabolic laboratory at Northwest University in Potchefstroom for analysis of metabolites. This will be done by performing mass spectroscopy, coupled with chromatography, followed by complex data analysis. The investigations at the metabolic laboratory will be performed and interpreted by Dr [name], from the biochemistry division at Northwest University. Stellenbosch University students will use aliquots of the CSF in future for unbiased evaluation of novel protein biomarkers that may be used in the diagnosis of TBM, for optimization of the test that will be developed as part of this project or biomarkers that may guide clinical patient management.

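### Aim 1 is to validate an existing three-marker CSF signature, but the analysis plan names only model-fitting methods for marker combinations and specifies no test of the existing rule

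*Combined protocol and SAP*

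**What the plan says.** The first item under Aims is "To validate a previously identified and patented three-marker CSF biosignature (IL-13, VEGF, cathelicidin LL37) for the diagnosis of TBM, in a new cohort". The background section on host biomarkers repeats the commitment ("We would specifically be validating the diagnostic accuracy of our previously established 3-marker TBM CSF biosignature") and gives the pilot performance: the signature "diagnosed TBM with a sensitivity of 52%, specificity of 95%, with positive and negative predictive values of 91% and 66% respectively". The section on collection and processing of samples mentions completed studies "which provided samples for the pilot studies leading to this validation study".

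The section Statistical methods and analysis plan is the only analysis text. For single markers it says: "The diagnostic accuracy of individual host biomarkers shall be investigated by receiver operator characteristics (ROC) curve analysis". For combinations it says that predictive ability "shall be investigated by General discriminant analysis (GDA), random forests, and other biomarker analysis techniques, following the training/test set approach" of previous studies, citing references 27 and 31 to 33. Reference 33 is the pilot.

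On numbers, section 3 (Inclusion and exclusion criteria) states that the sample size "required for each of the diagnostic aims of the study includes, at least, 72 children with definite or probable TBM", with a total of up to 460 children and about 40 new TBM admissions a year. It mentions no split into training and test parts.

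**The concern.** Validating an established diagnostic rule means applying it, with its weights and cut-off already fixed, to children who played no part in building it. General discriminant analysis and random forests do something else: they estimate a rule from the data supplied. The plan uses one sentence for every biosignature, so the existing signature of aim 1 is not separated from the search for new ones.

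If that sentence is carried out inside the new cohort, two things follow. The three markers receive new weights and a new cut-off, so the resulting sensitivity and specificity belong to a different rule and cannot be set against 52% and 95%. And accuracy is estimated only in the held-out children, which discards TBM cases that a locked rule could use. Validated markers are meant to go into the point-of-care prototype (section Ethical concerns and consent), so it matters which rule has been validated.

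**Working it through.** **1. The pilot figures.** They agree with one another. At a TBM share of 50%, sensitivity 52% and specificity 95% give PPV = 0.52×0.5 / (0.52×0.5 + 0.05×0.5) = 0.260/0.285 = 91%, and NPV = 0.95×0.5 / (0.95×0.5 + 0.48×0.5) = 0.475/0.715 = 66%. The plan therefore has a coherent benchmark for aim 1.

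**2. The planned 72.** This figure cannot be reproduced. The plan names a two-sample comparison of proportions but not the two proportions, power, sidedness or group ratio, and many pairs of proportions give 72. The present point does not depend on it.

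**3. What a fixed-rule test needs, against what the plan gives.**

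| Needed | In the documents |
|---|---|
| Pilot equation and cut-off | Not printed |
| Statement that the rule is applied unchanged | None |
| Children in whom it is assessed | Training/test approach; shares not given; not said whether training means the pilot or part of this cohort |
| Comparison with 52%/95% | None |
| Confidence intervals | None |

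**4. Precision lost through a split.** Inputs: 72 TBM cases (section 3) and sensitivity near 52% (background). The split shares are assumptions. Exact (Clopper-Pearson) limits for x positives out of n are the 2.5% quantile of Beta(x, n−x+1) and the 97.5% quantile of Beta(x+1, n−x).

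| TBM cases assessed | x/n | 95% interval |
|---|---|---|
| All 72 | 37/72 | 39.3% to 63.3% |
| Half held out | 19/36 | 35.5% to 69.6% |
| 30% held out | 11/22 | 28.2% to 71.8% |

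The width rises from 63.3 − 39.3 = 24.0 points to 69.6 − 35.5 = 34.1 points with half held out.

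For specificity, assume exactly 72 TBM cases in a full 460, leaving 460 − 72 = 388 others. All 388 give 369/388, 92.5% to 97.0%. Half give 184/194, 90.7% to 97.5%. The loss falls mainly on sensitivity.

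**5. If more cases are enrolled.** At an assumed 150 TBM cases the sensitivity intervals are 43.7% to 60.2% with all cases (78/150) and 40.2% to 63.7% with half held out (39/75). Having 72 cases in the held-out part alone would take 72/0.5 = 144 cases, or 72/0.3 = 240 with 30% held out. Section 3 gives about 40 admissions a year from November 2016 to December 2025. That is 110 months, so 40 × 110/12 ≈ 367 admissions before losses to consent, and the floor of 72 need not be the number reached.

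**The case against.** The strongest reply is that the plan takes its approach by citation from earlier studies that include the pilot. Training could mean the pilot cohort, with this cohort as the test set, and the unnamed other techniques could include a locked-rule test. That stands as a possible reading, and the cited papers were not available to settle it. But allowing an analysis is not the same as specifying it, and no sentence says that the existing rule will be applied unchanged.

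A second reply is that the documents identify the signature only by its three markers, so held-out accuracy of the same marker set might count as validation. The wording allows this weaker reading. It does not fit easily with a background section that speaks of the accuracy of an established signature and gives its operating characteristics.

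A reader might also infer that refitting is bound to move the results far because the TBM share falls from about 50% in the pilot to 72/460 = 16% here. The documents do not support this. The 16% divides a minimum by a maximum, and the stated case flow suggests that the share could be much higher. Nor can the size of any shift be predicted: the documents give neither the pilot cut-off nor the class priors a refit would use. The size of the change from refitting is unknown. Only its direct consequence, loss of comparability, is certain.

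**Conclusion.** The point holds as a gap in specification and should be fixed. Aim 1 promises validation of an existing rule, and the plan specifies no analysis that would deliver it. If the named methods are fitted within this cohort, the result cannot be read as confirming or refuting 52%/95%. At the floor of 72 TBM cases, holding out half would widen the interval for sensitivity from 39%–63% to about 35%–70%. That size rests on an assumed split and on the minimum case number; it shrinks as enrolment rises, though the loss of comparability does not.

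A reader might go further and conclude that the plan rules out a proper validation, or that the study is too small for one. Neither follows. The wording leaves room for a fixed-rule test, and the planned numbers can support one if all cases are used.

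**What to change.** Add a paragraph for aim 1 to Statistical methods and analysis plan:

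- Say whether training means the pilot or part of this cohort.
- Lock the pilot equation and cut-off before marker results are linked to diagnostic group, and apply them unchanged, without a split, to every eligible child with the three CSF markers measured.
- Report sensitivity and specificity with exact 95% intervals beside the pilot 52% and 95%.
- Report any recalibrated or refitted three-marker version as secondary.
- Keep the training/test approach for new signatures.

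A prestated criterion for calling the signature validated, and an AUC with its interval method, would be useful but are optional.

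The cost is protocol wording; no extra samples or assays are needed, because CSF is already stored for the same Luminex technology as the pilot. The change depends on the group still holding the pilot equation and cut-off. If these cannot be recovered, reword aim 1 as redevelopment of the signature. The downside is that a change of assay kit or lot may make the locked cut-off look worse than the markers deserve; the secondary recalibrated analysis covers this.
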